## 1 Introduction

### 1.1 Axitinib

Axitinib is an oral, potent and selective inhibitor of vascular endothelial growth factor (VEGF) receptors 1, 2, and 3. As of 27 August 2012, axitinib was approved in 6 countries (United States [US; January 2012], Switzerland [April 2012], Japan [June 2012], Canada [July 2012], Australia [July 2012] and Korea [August 2012]) for previously-treated patients with advanced renal cell carcinoma (RCC); the actual indication varies from country to country. The safety and efficacy of axitinib is being evaluated in patients with a variety of solid tumors, including in treatment-naïve patients with advanced RCC [Information from Investigator's Brochure, September 2012].

VEGF receptors are critical components of the processes leading to the branching, extension, and survival of endothelial cells which form new blood vessels during angiogenesis, an absolute necessity for tumor growth beyond microscopic size. In nonclinical tumor mouse models, twice-daily (BID) oral administration of axitinib demonstrated consistent and significant anti-tumor efficacy (marked inhibitory effect on local and distant tumor metastasis and prolonged animal survival). In multiple animal models, the combination of axitinib with various standard chemotherapies (e.g., docetaxel or carboplatin) and other antiangiogenic agents (e.g., bevacizumab) demonstrated improved benefit compared with single-agent chemotherapeutic/antiangiogenic agents.

The nonclinical safety profile of axitinib has been well characterized through the conduct of single-dose and repeat-dose toxicity studies of up to 39 weeks in duration, and safety pharmacology, genetic toxicity, reproductive and developmental toxicity, and phototoxicity studies. The primary target organ toxicities were observed in the gastrointestinal, hematopoietic, musculoskeletal, and reproductive systems. Additionally, hemodynamic effects (elevated blood pressure, reduced heart rate) were identified from repeat-dosing in conscious, telemetered animals. Axitinib was not identified as a mutagen or clastogen, but considered an aneugen at area under the plasma concentration-time curve (AUC) exposure that exceeds that at the recommended human dose (RHD) of 5 mg BID. While axitinib has relevant ultraviolet (UV) absorbance with the potential to distribute to sun-exposed tissues, no phototoxicity potential was identified from in vitro testing in 3T3 fibroblasts. Many of the findings identified from non-clinical safety testing are consistent with the anticipated pharmacological response to a VEGF receptor inhibitor, including the blood pressure changes, and effects on ovarian follicles and the growth plate of actively growing animals, which are reliant on angiogenesis for development. Fertility and developmental effects were also observed, consistent with the effects identified from toxicity studies on reproductive organs and role of angiogenesis in the development of a fetus.

Axitinib and its metabolites were widely distributed into tissues in mice, but did not accumulate and were not retained for long periods of time in most tissues. The plasma protein binding was 97%, 98%, and 99% in the mouse, dog, and human, respectively.

In humans, the median recovery of [C] axitinib radioactivity in feces was 37.0% and in urine was 22.7% (total recovery = 59.7%) of the total orally administered dose (5 mg). In plasma, the glucuronide was the predominant metabolite and accounted for approximately 50% of the circulating radioactivity. The sulfoxide and unchanged parent drug accounted for approximately 20% of the circulating radioactivity. In feces, the parent drug represented the single most predominant radioactive component (12% of the dose).

As of 1 June 2012, 43 studies evaluating the safety, efficacy, and PK of axitinib have been completed or are ongoing. These studies include 15 Phase 1 studies in healthy subjects and 28 studies in subjects with cancer including 1 continued access and 1 compassionate-use study.

A study in healthy volunteers (A4061007) indicated that the mean absolute oral bioavailability of the drug was 58%. Interaction studies in healthy volunteers with the CYP3A4/5 inhibitor ketoconazole (A4061004) and CYP3A4/5 inducer rifampin (A4061026) produced a 2-fold increase and 79% reduction in axitinib plasma exposures, respectively. Axitinib has two major (non-pharmacologically active) circulating plasma metabolites, a glucuronide product and a sulfoxide product (A4061003). In subjects with moderate hepatic impairment (Child Pugh B), there was a ~2-fold increase in axitinib area under curve from zero to infinity (AUC (0-∞)) and a 1.3-fold increase in axitinib maximum plasma concentration (Cmax) compared to subjects with normal hepatic function (A4061036). No difference in axitinib plasma pharmacokinetics was observed between Caucasian and first-generation Japanese volunteers (n=20 each) (A4061026). Phase 1 studies in combination with chemotherapeutic/anticancer agents in cancer patients have indicated plasma pharmacokinetics of docetaxel, paclitaxel, carboplatin, capecitabine, gemcitabine, cisplatin, pemetrexed, oxaliplatin, 5-fluorouracil (5-FU), bevacizumab, and irinotecan (including its SN-38 activated metabolite) were similar in the absence and presence of axitinib. Likewise, axitinib plasma profiles and pharmacokinetic parameters were similar in the presence and absence of these co-administered chemotherapeutic/anticancer agents (A4061019 and A4061020).

In ongoing clinical studies, the axitinib starting dose is 5 mg BID. Subjects who can tolerate axitinib with no adverse events related to axitinib above Common Terminology Criteria for Adverse Events (CTCAE) Grade 2 for consecutive 2 week periods are permitted to increase their dose step-wise to 7 mg BID and then to a maximum of 10 mg BID, unless their blood pressure (BP) is >150/90 mm Hg. The dose of axitinib can be reduced to as low as 2 mg BID if > Grade 2 treatment-related adverse events occur.

Overall, the adverse events reported for axitinib in clinical studies are considered manageable, generally reversible and expected for this class of agents. For single-agent axitinib, the most common adverse events (>20%) reported from 699 cancer subjects regardless of causality included diarrhea (397 subjects, 56.8%), fatigue (368 subjects, 52.6%), hypertension (318 subjects, 45.5%), decrease appetite (286 subjects, 40.9%), nausea (264 subjects, 37.8%), dysphonia (242 subjects, 34.6%), palmar-plantar erythrodysesthesia syndrome (202 subjects, 28.9%), weight decreased (197 subjects, 28.2%), vomiting (166 subjects, 23.7%), constipation (165 subjects, 23.6%), headache (151 subjects, 21.6%), cough (149 subjects, 21.3%), arthralgia and dyspnea (140 subjects, 20%). Grade 3+ events occurred most frequently for hypertension (134 subjects, 19.2%), fatigue (90 subjects, 12.9%), and diarrhea (65 subjects, 9.3%).

Hypothyroidism and proteinuria were reported as adverse events in 122/699 subjects (17.5%) and 117/699 subjects (16.7 %), respectively. Hemorrhagic events (including epistaxis, hematuria, hemoptysis, rectal hemorrhage, cerebral hemorrhage, gastric hemorrhage, and lower gastrointestinal hemorrhage) were reported in 182/699 subjects (26.0%); Grade 3+ hemorrhagic events occurred in 13/699 subjects (1.9%), including 1 death (gastric hemorrhage).

Arterial thromboembolic events (including cerebral infarction, cerebrovascular accident, embolism arterial, lacunar infarction, myocardial infarction, retinal artery occlusion, and transient ischemic attack) were reported in 16/699 subjects (2.3%) including 2 deaths (secondary to cerebrovascular accident). Venous thromboembolic events (including pulmonary embolism, deep vein thrombosis, retinal vein occlusion and jugular vein thrombosis) were reported in 21/699 subjects (3.0%) including 2 deaths (pulmonary embolism). Gastrointestinal perforation (including gastrointestinal perforation, large intestine perforation, and intestinal perforation) were reported in 5/699 subjects (0.7%) including 1 death (intestinal perforation). In addition to cases of gastrointestinal perforation, fistulas (including anal fistula and fistula) were reported in 4/699 subjects (0.6%). Reversible posterior leukoencephalopathy syndrome (RPLS) was reported in 3/699 subjects (0.4%).

Axitinib has been investigated in combination with various chemotherapy regimens (e.g., docetaxel, carboplatin/paclitaxel, gemcitabine, capecitabine/cisplatin, gemcitabine/cisplatin, weekly paclitaxel, capecitabine, FOLFIRI, FOLFOX, FOLFOX + bevacizumab, and pemetrexed/cisplatin). In general, axitinib at a starting dose of 5 mg BID administered continuously has been combined with the full dose of chemotherapy. Non-hematological safety events have been similar to those for the single-agent axitinib and those for the chemotherapy regimens. Preliminary evidence of antitumor activity has been observed with axitinib as a single agent and in combination with chemotherapy across multiple tumor types. Plasma concentrations as well as pharmacokinetic parameters of the co-administered chemotherapeutic/anti-cancer drug were similar in the presence and absence of axitinib. However, a clinical study conducted with axitinib in combination with docetaxel indicated that the docetaxel mean plasma exposure was increased in the presence of axitinib. The plasma pharmacokinetics of axitinib was similar in the presence of all chemotherapeutic agents evaluated.

A Phase 3 study comparing axitinib versus sorafenib in previously-treated (second-line) patients with advanced renal cell carcinoma (RCC) met the primary endpoint (progression-free survival [PFS] per blinded independent review). The most common ( $\geq 20\%$ ) adverse reactions observed following treatment with axitinib were diarrhea, hypertension, fatigue, decreased appetite, nausea, dysphonia, palmar-plantar erythrodysesthesia (hand-foot) syndrome, weight decreased, vomiting, asthenia, and constipation. Based on the findings from this registrational study, as of 27 August 2012, axitinib was approved in 6 countries (United States [US; January 2012], Switzerland [April 2012], Japan [June 2012], Canada [July 2012], Australia [July 2012] and Korea [August 2012]) for previously-treated patients with advanced renal cell carcinoma (RCC); the actual indication varies from country to country. A Phase 3 study comparing axitinib vs sorafenib in treatment-naïve (first-line) patients with advanced RCC is ongoing. A double-

blind randomized Phase 2 study comparing dose titration with axitinib vs placebo in treatment-naïve (first-line) patients with advanced RCC is also ongoing.

In addition, a double-blind randomized study comparing axitinib vs placebo in previously-treated (second-line) patients with advanced hepatocellular carcinoma (HCC) is ongoing. Phase 1 and 2 studies are ongoing in other advanced solid tumors. Combination studies of axitinib with chemotherapy are being conducted in non-small cell lung cancer (NSCLC), colorectal cancer (CRC), and gastric cancer.

### *Pediatric Studies*

The Children's Oncology Group phase 1 study ADVL1315 (NCT02164838) for pediatric patients with recurrent/refractory solid tumors recently determined a recommended phase 2 dose (RP2D) of 2.4 mg/m^2 PO BID, corresponding to approximately 4mg PO BID in an average sized adult, or 80% of the adult standard starting dose [J Clin Oncol 34, 2016 (suppl; abstr 10558)]. In this study, oral axitinib tablets were administered twice daily, continuously in 28-day cycles. Dose levels 2.4 and 3.2 mg/m^2/dose were evaluated using a rolling 6 design. As of December 11, 2015, 17 patients were enrolled with 1 ineligible (inadequate time from prior therapy). The median age was 14 yrs (range 5–17 yrs); 9 were male. Patients received a median 3 prior chemotherapy regimens (range 1-8). Cancer diagnoses included soft tissue sarcomas (7), Ewing (2) and osteosarcoma (1), neuroblastoma (2), Wilms tumor (1), hepatoblastoma (1), hepatocellular carcinoma (1), medullary carcinoma (1), and epithelial-myoeithelial carcinoma (1). Toxicity data were available for 15 patients (6 at dose level 1, 5 at dose level 2, and 4 on an expanded PK cohort). One patient was inevaluable for toxicity due to inadequate drug exposure. DLTs occurred in 0/6 and 2/5 patients treated at dose level 1 and 2 respectively (palmar-plantar erythrodysesthesia syndrome (1); intratumoral hemorrhage (1)). Cycle 1 hematologic toxicities included grade 3 lymphopenia (1) and grade 1 or 2 anemia (4), lymphopenia (3), elevated hemoglobin (3), leukopenia (2), neutropenia (1), thrombocytopenia (1), and lymphocytosis (1). Non-hematologic toxicities included grade 1 or 2 nausea (5), hypertension (4), anorexia (3), creatinine elevation (2), diarrhea (2), fatigue (2), headache (2), lipase elevation (2), proteinuria (2), and acneiform rash (2). The most common subsequent cycle grade 3 or 4 toxicities included neutropenia (grade 3 (3), grade 4 (1)) and lymphopenia (grade 3 (1), grade 4 (1)).

## **1.2 Neurofibromatosis Type 2 (NF2) and Study Rationale**

Neurofibromatosis type 2 (NF2) is an autosomal-dominant genetic disease with an incidence of approximately 1/40,000. The NF-2 gene is located on chromosome 22 and its gene product is named Merlin. Merlin's function is not well understood, but it appears to act as a tumor suppressor. The majority of NF2 patients develop progressive hearing loss in adolescence or young adulthood due to unilateral or bilateral vestibular schwannomas (VS). Spinal tumors, including meningiomas, schwannomas and ependymomas, as well as intracranial tumors, mostly meningiomas, are also highly prevalent. NF2-related tumors, although mostly slow growing, cause considerable morbidity and mortality, particularly when first diagnosed at a young age. The available treatment options for these neoplasms, which often occur at multiple sites simultaneously, are non-curative and mostly limited to surgery and radiation therapy. As

a result, all NF2 patients suffer from major morbidity, mortality and significantly reduced life expectancy.

Although classic chemotherapy is effective treatment for low-grade brain tumors, no such therapy has been validated for NF2 patients with multiple tumors for a variety of reasons. Most chemotherapeutic agents are mutagenic and there is reluctance to use them in patients with loss of tumor-suppressor function, such as NF2. Many chemotherapeutic drugs are neuro- and/or ototoxic, making them unsuitable for NF2 patients. No chemotherapy regimens have been identified to date for the most common tumors arising in NF-2 patients such as meningiomas, ependymomas and schwannomas. Surgery remains the mainstay of therapy for VS, but carries major risks including complete deafness, facial palsy, stroke and CSF leak. Medical treatment options for VS are therefore urgently needed.

Although VS and meningiomas are the hallmark of NF2, the vast majority of VS and meningiomas arise sporadically in non-NF2 patients. The prevalence of idiopathic VS in the US is roughly 3,000 new cases per year and the incidence appears to be increasing in recent years. These tumors cause unilateral hearing loss, tinnitus, imbalance and vertigo. The primary treatment modality for these tumors is surgical resection or radiosurgery. Surgery can be associated with the same complications listed above for NF2-related VS. Hence, RT is often offered in place of surgery. Although considered safer in idiopathic VS, long term efficacy has not been established and RT may complicate future procedures. Therefore, this large population of patients with sporadic VS may also benefit from a medical option either at initial diagnosis or at progression.

Axitinib is an oral multi-receptor tyrosine kinase (RTK) inhibitor targeting vascular endothelial growth factor receptor (VEGFR), platelet derived growth factor receptor (PDGFR), and c-KIT. Axitinib inhibits VEGFR1/2/3, PDGFR $\alpha/\beta$  and c-KIT phosphorylation in the sub- to low nanomolar range. Axitinib is currently FDA-approved for the second-line treatment of renal cell carcinoma. All of the molecular targets of axitinib represent clinically and/or preclinically validated molecular targets for VS:

**VEGFR:** Angiogenesis occurs in VS, and VEGFRs are expressed in these tumors. Anti-VEGF(R)-directed therapy with bevacizumab and vandetanib normalized the vasculature of NF2-/- schwannoma xenografts in nude mice and decreased tumor growth. Clinically, VEGF-targeted therapy with bevacizumab has been reported to lead to dramatic tumor shrinkage and hearing improvement in NF2 patients with VS. Sporadic responses of meningiomas to bevacizumab have been reported, and trials with angiogenesis inhibitors for sporadic meningiomas are ongoing.

**PDGFR $\beta$ :** Schwann cells express PDGFR $\alpha$  and PDGFR $\beta$ . Signaling through these receptors activates the RAS-RAF-MEK-ERK and PI3K-AKT signaling pathways, and is important for Schwann cell proliferation *in vivo* and *in vitro*. Overexpression of PDGFR $\beta$  has been observed in VS, and PDGFR inhibitors including AG1296, imatinib and nilotinib are effective in preventing PDGFR-driven proliferation when tested in VS *in vitro* models.

**c-KIT:** VS express activated c-KIT and are growth-inhibited by imatinib and nilotinib.

**In summary, the molecular target profile of axitinib makes it a promising drug candidate for clinical study in NF2 patients with progressive VS.** Although the potency of axitinib in inhibiting PDGFR and c-KIT is significantly lower than VEGFR1/2/3, preclinical data indicates accumulation of axitinib in brain tissue, and similarly, we have observed tumor tissue to plasma ratio of 4.3 +/-1.9 in human VS tissue treated with the EGFR/ErbB2 receptor tyrosine kinase inhibitor lapatinib (Karajannis, et. al, *Neuro-Oncology* 14:i19, 2012 [abstract]).

The favorable toxicity profile and tolerability of axitinib compared to other multi-kinase inhibitors is advantageous for potential long-term administration in NF2. Over the past 4 years, we have shown that we can successfully conduct and complete single-institution Phase 2 clinical trials in the NF2 population using molecular targeted agents including lapatinib and everolimus (ClinicalTrials.gov NCT00973739 and NCT01419639).

## 2 Key Eligibility Criteria

- 1) Age  $\geq$ 5 years
- 2) Clinically (NIH or Manchester criteria) or genetically confirmed diagnosis of NF2
- 3) Karnofsky (for >16 years) or Lansky ( $\leq$ 16 years) performance status of  $\geq$ 60
- 4) Disease criteria:
  - At least one volumetrically measurable NF2-related VS (histological confirmation not required)
  - MRI evidence of progression over the past 18 months, OR progressive hearing loss
- 5) Adequate organ system function (bone marrow, renal, hepatic)

## 3 Research Strategy

**Primary Objective:** To estimate the objective volumetric response rates to axitinib in pediatric and adult NF2 patients with VS.

**Secondary Objectives:** To assess the toxicity of axitinib given daily in patients with NF2 and to examine the association of objective measures of response on MRI, i.e. volumetric tumor analysis with clinical measures of response, i.e. (audiogram), as well as quality of life assessments (NFTI-QOL). In addition, response in non-VS tumors, such as other schwannomas and meningiomas, may be explored.

**Drug Dosage and Administration (adult patients, age  $\geq$ 18 years):** 5 mg axitinib PO BID, with increase to 7 mg PO BID and 10 mg BID after 2 and 4 weeks, respectively, provided no adverse reactions (i.e., not exceeding grade 2 toxicities) and normotensive and not receiving antihypertension medications. Axitinib will be given continuously in 28-day cycles.

**Drug Dosage and Administration (pediatric patients, age <18 years):** 2.4 mg/m^2 axitinib PO BID, with increase to 3.2 mg/m^2 PO BID after 2 weeks, provided no adverse reactions (i.e., not exceeding grade 2 toxicities) and normotensive and not receiving antihypertensive medications. Axitinib will be given continuously in 28-day cycles using a dosing nomogram shown in Section 7.3.1. The maximal dose of 3.2 mg/m^2 PO BID exceeds the recommended phase 2 dose from the pediatric phase 1 trial, with the rationale that young NF2 patients, who

are generally not pre-treated with myelotoxic chemotherapy are likely to tolerate a higher dose of axitinib compared to the heavily pre-treated, refractory cancer patients enrolled on the pediatric phase 1 study [J Clin Oncol 34, 2016 (suppl; abstr 10558)]. Similar to adult patients on this study, the option to escalate the dose is intended to optimize secondary target inhibition and therefore increase the likelihood of responses.

**Study Assessments:** MRIs including volumetrics and audiograms at baseline and after every 3rd cycle (i.e. 12 weeks). Monthly study visits including H&P, neurological examination and standard laboratory evaluations. Quality of life assessments (NFTI-QOL) at baseline and cycle 6.

**Treatment Duration:** Until radiographic progression or unacceptable toxicity.

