### **Exclusion criteria**

- Patients currently receiving medical anticancer therapies or who have received medical anticancer therapies within 4 weeks of the start of study drug (including chemotherapy, antibody based therapy, etc.)
- Radiation therapy to a study target tumor within 1 year prior to enrollment, or any radiation therapy within 4 weeks prior to enrollment.
- Patients who have had a major surgery or significant traumatic injury within 4 weeks of start of study drug, patients who have not recovered from the side effects of any major surgery (defined as requiring general anesthesia) or patients that may require major surgery during the course of the study
- Prior treatment with bevacizumab or other agents targeting VEGF or VEGFR

- Prior treatment with any investigational drug within the preceding 4 weeks
- Unstable or rapidly progressive disease, including patients who require glucocorticoids for symptomatic control of brain or spinal tumors
- Treatment with strong CYP3A4 enzyme inhibitors or inducers, including but not limited to ketoconazole, itraconazole, ritonavir, phenytoin, carbamazepine, rifampin, rifabutin, phenobarbital and St. John's wort. Please refer to the list in Appendix I.
- Requirement of therapeutic anticoagulant therapy with oral vitamin K antagonists; low-dose anticoagulants for maintenance of patency of central venous access device or prevention of deep venous thrombosis is allowed; therapeutic use of low molecular weight heparin (or similar parenteral drug) for venous-thromboembolic disease is allowed.
- Other malignancies within the past 3 years except for adequately treated carcinoma of the cervix or basal or squamous cell carcinomas of the skin.
- Patients who have any severe and/or uncontrolled medical conditions or other conditions that could affect their participation in the study such as:
  - Symptomatic congestive heart failure of New York heart Association Class III or IV
  - unstable angina pectoris, symptomatic congestive heart failure, myocardial infarction within 6 months of start of study drug, serious uncontrolled cardiac arrhythmia or any other clinically significant cardiac disease
  - severely impaired lung function as defined as spirometry and DLCO that is 50% of the normal predicted value and/or O2 saturation that is 90% or less at rest on room air
  - active (acute or chronic) or uncontrolled severe infections

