  - liver disease such as cirrhosis or severe hepatic impairment (Child-Pugh class C).
- Impairment of gastrointestinal function or gastrointestinal disease that may significantly alter the absorption of axitinib (e.g., ulcerative disease, uncontrolled nausea, vomiting, diarrhea, malabsorption syndrome or small bowel resection)
- Patients with an active bleeding diathesis
- Female patients who are pregnant or breast feeding, or adults of reproductive potential who are not using effective birth control methods. Adequate contraception must be used throughout the trial and for 8 weeks after the last dose of study drug, by both sexes. (Females of childbearing potential must have a negative serum pregnancy test within 7 days prior to administration of axitinib)
- Male patient whose sexual partner(s) are women of child bearing potential, who are not willing to use adequate contraception, during the study and for 8 weeks after the end of treatment
- History of noncompliance to medical regimens
- Patients unwilling to or unable to comply with the protocol

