**Pediatric Patients (<18 years of age)**

- **Starting dose (dose level 0):** 2.4 mg/m^2 PO twice daily (approx. 12 hours apart)
- **Dose titration:** Pediatric patients who tolerate axitinib with no adverse events related to axitinib above CTCAE Grade 2 for 2 weeks, are normotensive, and are not receiving anti-hypertension medication, should have their dose increased by one dose level (Dose level + 1, 3.2 mg/m^2/dose). Hypertension in the pediatric patients is defined as systolic or diastolic BP >95th percentile for age, height, and sex. Axitinib dose should be individually titrated up or down from the starting dose based on patient tolerance. Dosing will be based using a nomogram as shown below:

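### Children who pass the gate should go to 3.2 mg/m² BID, above the recommended pediatric dose, and no protocol text makes anyone reconsider the next child after an intratumoral hemorrhage

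*Combined protocol and SAP*

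**What the plan says.** **Dose.** Under Section 7.3.1 a child starts at 2.4 mg/m² BID. After 2 weeks with no related event above grade 2, with normal blood pressure and no antihypertensive drug, such children "should have their dose increased by one dose level (Dose level + 1", which is 3.2 mg/m². The same paragraph adds: "Axitinib dose should be individually titrated up or down from the starting dose based on patient tolerance".

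**Rationale.** Section 3 states openly that 3.2 mg/m² exceeds the recommended phase 2 dose. It argues that young NF2 patients, most of whom have had no prior treatment that harms the marrow, "are likely to tolerate a higher dose of axitinib compared to the heavily pre-treated, refractory cancer patients enrolled on the pediatric phase 1 study". It adds that escalation is meant to improve inhibition of the secondary targets.

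**Evidence.** The Pediatric Studies part of Section 1.1 reports for the phase 1 study: "DLTs occurred in 0/6 and 2/5 patients treated at dose level 1 and 2 respectively (palmar-plantar erythrodysesthesia syndrome (1); intratumoral hemorrhage (1". Its two dose levels were 2.4 and 3.2 mg/m².

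**Protection of the individual child.**
- The escalation gate, and visits at weeks 1, 2 and 3 of cycle 1 (Section 7.4.1).
- Grade-based dose rules (Section 7.3.3), and interruption for bleeding that needs intervention (Section 7.3.4).
- Exclusions, among them "Patients with an active bleeding diathesis", therapeutic vitamin K antagonists, and "Unstable or rapidly progressive disease, including patients who require glucocorticoids for symptomatic control of brain or spinal tumors".

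**Protection at trial level.**
- SAEs go to the FDA, the IRB and Pfizer, with a 24-hour clock for Pfizer (Section 7.4.5).
- The investigator or Pfizer may act at once for safety (Section 8).
- The DSMC reviews safety at least yearly and at the 9-patient interim, under its Charter (Section 12.1). It may recommend changes when it sees a safety concern (Section 12.2).

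**The concern.** The argument from lighter pre-treatment bears most directly on marrow reserve. The two phase 1 DLTs at 3.2 mg/m² were hand-foot syndrome and bleeding into a tumor, and the rationale mentions neither. The second matters here because every enrolled child carries at least one measurable vestibular schwannoma of 1 cc or more (Section 7.2.2).

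The patient-level rules deal with the child who has the event. They do not address the next child, who under Section 7.3.1 still should escalate. SAE routing in Section 7.4.5 does not name the DSMC. The general clauses in Sections 8 and 12.2 name no event, dose level or age group. As the protocol reads, later children can therefore keep moving to 3.2 mg/m² after a tumor hemorrhage at that dose, until someone uses discretion or a scheduled review falls due. What is at stake is the safety of minors at a dose knowingly set above the recommended one.

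**Working it through.** **1. The plan's own stopping figure.** The only defined halt is the Simon stage 1 rule: stop if there are 0 responses in 9 patients. The stated probability of early termination at a 5% response rate reproduces: 0.95^9 = 0.63. This rule concerns lack of response. Section 13 contains no toxicity rule.

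**2. Phase 1 DLTs** (inputs from Section 1.1, Pediatric Studies).
- 3.2 mg/m²: 2/5 = 40%, Clopper-Pearson 95% CI 5.3% to 85.3%.
- 2.4 mg/m²: 0/6 = 0%, upper limit 1 − 0.025^(1/6) = 45.9%.
- Fisher exact test, with 2 DLTs among 11 patients: P(both at 3.2) = C(5,2)/C(11,2) = 10/55 = 0.182. The opposite extreme, both at 2.4, has probability C(6,2)/C(11,2) = 15/55 = 0.273. This is larger, so it does not add to the two-sided p, which is 0.18.

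The data neither establish an excess at 3.2 mg/m² nor exclude a high rate there.

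**3. Does any text make someone decide about the next child?**

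| Provision | Prompted by | Acts on |
|---|---|---|
| Gate and titration, 7.3.1 | That child's tolerance | That child |
| Dose modification, 7.3.3 and 7.3.4 | That child's toxicity | That child |
| SAE reporting, 7.4.5 | Any SAE | Informs FDA, IRB and Pfizer; DSMC not named; no hold |
| Immediate safety action, 8 | Discretion | Whatever is chosen |
| DSMC review, 12.1 | At least yearly, and the interim | Trial |
| Safety clause, 12.2 | DSMC judgment | Trial |
| Recruitment halt, 12.2 and 13 | No response | Trial |

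No row links a toxicity event at level +1 to a required decision on further pediatric escalation.

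**4. How often would a hemorrhage hold fire?** With n escalated children and a per-child rate h, P = 1 − (1 − h)^n. The documents give no number of children, only a cap of 17 evaluable patients of all ages, so n = 3 and n = 6 are assumptions.
- Low case, h = 13/699 = 1.86%. This is the adult grade 3+ hemorrhage rate at any site (Section 1.1), used as an assumed rate. n = 3: 1 − 0.9814^3 = 5%. n = 6: 1 − 0.9814^6 = 11%.
- High case, h = 1/5, the phase 1 count for this event at 3.2 mg/m². n = 3: 1 − 0.8^3 = 49%. n = 6: 1 − 0.8^6 = 74%.

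**5. Optional count rule for other DLT-type events: 2 among the first 6 escalated children.** P = 1 − (1 − p)^6 − 6p(1 − p)^5. At assumed rates p of 10%, 20% and 40% this gives 11%, 34% and 77%. Event definition matters. If grade 3 hypertension counted, at the adult grade 3+ rate of 134/699 = 19.2%, it alone would reach 2 events in 6 children with probability 32%.

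**The case against.** **The Charter may close the gap.** Section 12.1 places DSMC reviews under a Charter that is not among these documents, and event-driven review could well be there. This stands. It limits the point to the protocol text and makes a Charter citation a full answer.

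**Oversight is not absent.** The DSMC clause in Section 12.2 is conditional on a concern and not tied to the calendar. A serious hemorrhage would reach Pfizer within 24 hours. A reader might infer that there is no trial-level safety oversight, and the documents contradict that. What remains is that these provisions permit a decision on the next child without requiring one.

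**The dose is not extreme.** Section 1.1 equates 2.4 mg/m² with about 4 mg BID in an average-sized adult. In proportion, 3.2 mg/m² is 4 × 3.2/2.4 = 5.3 mg, close to the adult starting dose of 5 mg. The pediatric level +1 table tops out at 6 mg BID, below the first adult escalation to 7 mg. This is fair context, but it does not answer two DLTs in five pediatric patients.

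**The rationale is wider than marrow.** Section 3 also contrasts NF2 children with refractory cancer patients, and NF2 tumors are mostly slow growing (Section 1.2), which could bear on bleeding risk. That is plausible, but Section 3 does not make the argument.

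**The numbers are weak.** A reader might infer that 40% of children here would have a DLT, or that 3.2 mg/m² is shown to be more toxic than 2.4. Neither follows. The interval runs from 5% to 85%, p is 0.18, and children here first tolerate 2.4 mg/m² for 2 weeks, so 40% may overstate their rate. The adult rates carry no time window, and the 10% and 20% rates in the count rule have no source. For these reasons the count rule is offered only as an option.

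**Conclusion.** The point holds as a gap in the protocol text and warrants a change. Eligible children should escalate above the recommended dose. The only pediatric data cited at that dose include an intratumoral hemorrhage (2/5 DLTs overall, 95% CI 5% to 85%). The rationale does not discuss those DLTs, and nothing written requires a decision about the next child after one.

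The documents do not support a stronger conclusion that escalation should be dropped. The imprecision of 2/5, the tolerance gate and the individual dose rules argue for a checkpoint, not a ban.

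Confidence is medium. The conclusion assumes that the Charter has no such trigger. The firing probabilities depend on assumed numbers of children and on rates carried over from adults or from one event in five patients.

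**What to change.** 1. **Sections 7.4.5 and 12.1.** For a child at level +1, add the DSMC to the existing 24-hour reporting for (a) any intracranial or intratumoral hemorrhage and (b) any other related, DLT-type non-hematologic SAE.
2. **Section 12.2.** After any event under (a), hold further pediatric escalation until the DSMC has reviewed it. Children not yet escalated stay at 2.4 mg/m² meanwhile. If the Charter already requires this, cite the clause instead.
3. **Optional.** A count rule for (b), for example 2 in the first 6 escalated children. The sponsor and DSMC should set the definition, window and count, leaving out grade 3 hypertension controlled with standard management. One sentence in Section 3 could say why the two DLTs do not rule out escalation.

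**Cost.** Amendment wording or a citation, using the existing committee, with no extra patients, visits or procedures. The downside is an occasional pause that proves unneeded: for the hemorrhage hold alone, about 5% with 3 children and 11% with 6 at the assumed 1.9% rate. During a pause, treatment continues at the recommended pediatric dose for children not yet escalated.
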